Eligibility. Criteria for inclusion in this portion of the study are: (1) Male, (2) age 18 or older, (3) fluent in English, (4) self-reported unprotected anal sex with a casual male partner at least once in the past 3 months¹², (5) heavy alcohol use during the past 2-weeks (>14 drinks per week, or at least one occasion of 5+ drinks)¹³, (6) register a breath alcohol content of .000 upon recruitment, (7) no history of complex alcohol withdrawal, (8) scoring < 4 on severity of dependence scale (SDS) for methamphetamine¹⁴, and < 3 on the SDS for cocaine and heroin/opiates^{15; 16}, (9) HIV-negative as indicated during their preliminary HIV testing, and (10) willing to provide phone and email contact information (see Design Considerations section below for further detail). Participants who test HIV+, score highly on the SDS, or participated in Phase 1 of the research will be excluded from participation. Those testing HIV+ will be referred to a comprehensive care clinic at the Miriam Hospital for treatment, as per the standard protocol of our collaborating agency. Those with high SDS scores will be provided with lists of local MSM-friendly drug treatment providers.

Recruitment. We will recruit participants from among those seeking HIV testing at the identified community-based venues. Patrons who are interested in participating indicate this on

their standard HIV testing “exit” form, which is anonymous. After APRI staff deliver negative results, participants will remain in a private room, where our research study staff will enter and provide further information about the study.

Baseline Assessment. All assessments will be completed on the tablet and administered by a research assistant that is blind to experimental condition. Study staff will first acquire informed consent and deliver the tablet to begin collecting baseline/screening measures. While ineligible participants will be informed of this on the assessment screen, eligible participants will then proceed directly to complete other baseline measures. Participants will receive \$50 for the baseline session, which may take up to 90 minutes.

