Baseline/Eligibility Assessments. The SDS¹⁷ will be used to assess symptoms of substance dependence for methamphetamine, cocaine, heroin/opiates, and alcohol. The SDS has demonstrated good validity and excellent reliability with respect to these drugs ($\alpha=0.80-0.85$)^{14; 15; 17}. In addition, a 30-day Timeline Follow Back (TLFB)^{18; 19}, administered online, will be used to assess alcohol use and sexual behavior during that period. The TLFB presents a calendar of each recall period, and participants respond by clicking on a box that represents a given day, answering several questions about that day. Questions will assess the number of standard drinks consumed on that day, the number of hours over which these drinks were consumed, the total number of sex partners, their relationship with each (e.g., steady vs. casual), the HIV status of each (e.g., HIV+, HIV-, or unknown), whether they asked about their partner’s HIV/STI status or the last time they were tested, sex acts performed with each, condom use for each act, and whether sexual activity took place while under the influence of alcohol. Meta-analyses have shown that TLFBs for assessing alcohol use and sex behavior are reliable when administered electronically and online²⁰. Other studies explicitly comparing online vs. in-person TLFBs for sexual behavior²¹, and comparing the TLFB to biological measures for alcohol use²² have confirmed the validity of online TLFBs. TLFB data will be used to determine participants’ drinking eligibility, while single items will assess all other eligibility criteria. Finally, stages of change will be assessed using the Stages of Change (Short Form)²³ and a 4-item stages of change measure for HIV-risk²⁴⁻²⁶.

Efficacy outcomes. Our primary outcomes will be the number of unprotected anal sex events, number of sex events under the influence of alcohol, frequency of drinking, and the

number of heavy drinking days over the past month. Outcomes will be assessed via 30-day Timeline Follow Back (TLFB)^{91, 93} at each follow-up.

Secondary outcomes. We will also assess whether participants talked to their partners about their HIV/STI status and recent testing, and whether during each follow-up window, participants engaged in self-initiated HIV testing, sought STI screening, or sought information about pre-exposure prophylaxis. Change motivation and stages will also be explored as secondary outcomes.

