Primary analyses. Our hypotheses related to Specific Aim 2 are that participants in the intervention group will report (1) fewer unprotected anal sex events, (2) fewer events involving sex while under the influence of alcohol, and (3) lower frequency of drinking and a reduced number of heavy drinking days versus the control group. These hypotheses will be evaluated using an intention-to-treat comparison of the rates of our primary outcomes at 1-, 3-, and 6-month follow-ups, using an incidence rate ratio (IRR) and 95% CI. Given the count nature of the data, we will use a Poisson regression covarying for key baseline covariates, and compare IRRs across the two treatment conditions at each time point. As conclusions about statistical significance will be limited due to the small sample, clinically meaningful differences in the pattern of IRRs and means (for alcohol use variables) across groups will be used to evaluate our hypotheses. However, if available data produce stable results, generalized estimating equations (GEEs) using binomial distributions and logit-link functions will also be used to explore differences in these outcomes across time and treatment condition. We will also explore the potential influence of the intervention on secondary outcomes and exploratory mediators. IRRs and descriptive data will be used to compare the groups in terms of their frequency of talking to partners about their status, whether they sought additional HIV testing, STI screening or information about PrEP. Descriptive mean comparisons and linear regressions controlling for baseline values will be used to compare whether HIV knowledge and perceived risk, peer safe sex norms, and safe sex behavioral skills differ across the groups.

C.4.3. Recruitment

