## **STATISTICAL ANALYSIS PLAN**

**Title:** Brief Electronic Intervention for Heavy Drinking and Sex Risk Among Men who have sex with Men  
Seeking HIV Testing

**NCT#:** NCT03435783

**Date of document:** Last reviewed and approved by Brown IRB on 7/21/17

**Statistical analysis plan.** We hypothesized that participants using the web-based intervention would report (1) fewer new anal sex partners, (2) fewer condomless anal sex events, and (3) lower frequency of drinking, (4) lower frequency of binge drinking, and (5) a lower average number of drinks per drinking day versus the control group. These hypotheses will be evaluated using an intention-to-treat comparison of the rates of our primary outcomes at 1-, 2-, and 3-month follow-ups, using incidence rate ratios (IRRs) and 95% CI. Given the count nature of much of the data, we will use a Poisson regression covarying for key baseline covariates, and compare IRRs across the two treatment conditions at each time point. As conclusions about statistical significance will be limited due to the small sample, clinically meaningful differences in the pattern of IRRs and means (for alcohol use variables) across groups will be used to evaluate our hypotheses. However, if available data produce stable results, generalized estimating equations (GEEs) using binomial distributions and logit-link functions will also be used to explore differences in these outcomes across time and treatment condition. We will also explore the potential influence of the intervention on secondary outcomes and exploratory mediators. IRRs and descriptive data will be used to compare the groups in terms of their frequency of talking to partners about their status, whether they sought additional HIV testing, STI screening or information about PrEP. Descriptive mean comparisons and linear regressions controlling for baseline values will be used to compare whether HIV knowledge and perceived risk, peer safe sex norms, and safe sex behavioral skills differ across the groups.

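### The primary Poisson regression makes no allowance for extra-Poisson variation, so 95% CIs for sexual event counts are likely too narrow; for days out of 30 the error can go either way

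*SAP*

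**What the plan says.** The SAP's single paragraph gives the primary method: "Given the count nature of much of the data, we will use a Poisson regression covarying for key baseline covariates". The arms are compared by IRRs with 95% CIs at each follow-up. The protocol (C.4.2.2 Data Analysis Plan, Primary analyses) is almost identical: "Given the count nature of the data, we will use a Poisson regression covarying for key baseline covariates". Neither document says how standard errors are obtained, mentions over-dispersion, or lists the covariates, so adjustment for an outcome's own baseline value is not assured.

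Other relevant text:

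- The SAP's five primary outcomes are new anal sex partners, condomless anal sex events, drinking frequency, binge frequency, and "a lower average number of drinks per drinking day versus the control group". The last is a mean, not a count, and no other regression model is named for it.
- Protocol C.4.2.2 Measures (Efficacy outcomes) takes outcomes from a 30-day Timeline Follow Back (TLFB), so drinking days and heavy drinking days cannot exceed 30.
- Protocol C.4.2.1 Methods (Eligibility) requires "self-reported unprotected anal sex with a casual male partner at least once in the past 3 months" and sets no upper limit on acts or partners.
- The SAP adds that "conclusions about statistical significance will be limited due to the small sample" and that the pattern of IRRs and means will be judged instead.
- If results are stable, "generalized estimating equations (GEEs) using binomial distributions and logit-link functions will also be used to explore differences".
- IRRs and descriptive data are also planned for yes/no secondary outcomes: "whether they sought additional HIV testing, STI screening or information about PrEP".

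**The concern.** Model-based Poisson standard errors assume that, given the covariates, variance equals the mean. If men differ in their underlying rates beyond what the covariates explain, the variance is larger and the intervals are too short. The entry rule admits men with one unprotected act in three months alongside men with very many, so this is likely for sexual counts. Eligibility permits that spread; it does not prove it.

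Day counts differ because they are capped. If men are alike after adjustment, days out of 30 vary less than Poisson and the intervals are too wide. If men differ, they can be too narrow.

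Formal significance is already set aside, so the 95% CI is the only stated measure of how uncertain each IRR is. Specific Aim 2 uses these data to prepare a larger trial, and overstated precision would carry into that planning.

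**Working it through.** **Inputs from the documents.** N = 40 (Protocol C.4.2, Phase 2), 95% CIs, and a 30-day window for day counts. No event rate, variance, dispersion or drop-out figure is given, and N = 40 has no derivation to reproduce.

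**Assumptions.** 1:1 allocation (20 per arm; the ratio is not stated), no drop-out, no treatment effect, and a range of variance-to-mean ratios (VMR).

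**1. Analytic coverage.** If the residual VMR after covariates is φ, a nominal 95% Poisson interval covers 2Φ(1.96/√φ) − 1:

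| Residual VMR | Actual coverage |
|---|---|
| 1 | 95% |
| 1.5 | 89.0% |
| 2 | 83.4% |
| 3 | 74.2% |
| 4 | 67.3% |

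**2. Illustration.** Take 20 per arm, mean 4 events and IRR 1, so 80 events per arm. SE of log IRR = √(1/80 + 1/80) = 0.158.

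- Plain Poisson: exp(±1.96 × 0.158) = 0.73 to 1.36.
- Scaled, residual VMR 3, t with 37 df: exp(±2.026 × 0.158 × √3) = 0.57 to 1.74.
- Scaled, residual VMR 2: exp(±2.026 × 0.158 × √2) = 0.64 to 1.57.

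**3. Event counts, simulated with baseline adjustment.** Log-normal-Poisson data, means 2, 4 and 8, covariate log(baseline + 0.5), 3,000 runs per case. The VMR here is marginal, before adjustment, so it is not on the scale of step 1. Plain Poisson coverage:

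| Marginal VMR | Baseline correlation 0.5 | Baseline correlation 0.8 |
|---|---|---|
| 1.5 | 89-90% | 90-91% |
| 2 | 84-86% | 87-88% |
| 3 | 77-79% | 82-83% |
| 4 | 70-73% | 77-80% |

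With VMR 1, coverage is 95-96%. Pearson-scaled standard errors with a t reference gave 94-96%. A second data model (negative binomial, mean 2-3, size parameter 0.5-2, 1,500 runs) gave 61-87% for plain Poisson and 93-96% after scaling.

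**4. Days out of 30.** Binomial(30, p) data, with men's expected days uniform over a range. Plain Poisson coverage:

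| Range of expected days | Corr. 0.5 | Corr. 0.8 | Corr. 0.9 |
|---|---|---|---|
| 2-30 | 70% | 82% | 90% |
| 8-24 | 88% | 94% | 96% |
| 10-20 | 96% | 96% | 97% |
| 12-18 | 98% | 98% | 98% |

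Scaled standard errors gave 95-97%. A beta-binomial formula shows why the direction changes: VMR = (1 − p)(1 + 29ρ), where ρ is the within-man correlation. This exceeds 1 once ρ > p/(29(1 − p)), which is 0.009 at p = 0.2 and 0.023 at p = 0.4. Little residual difference between men is needed, particularly for infrequent behaviours such as binge days.

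**5. Yes/no secondary outcomes.** If their ratios come from a Poisson model (the SAP does not say), the standard error is too large by a factor 1/√(1 − p): 1.05, 1.12 and 1.41 at risks 0.1, 0.2 and 0.5.

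**The case against.** The strongest reply is that the plan is silent on the variance estimator and does not actually choose model-based errors; an analyst could use robust ones. That is fair as a reading of the text, but the default from a Poisson regression as written is the model-based interval, and a SAP should settle this before the data are seen.

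Second, every dispersion figure is assumed. That stands: the omission is certain, but the size of the error is not. The residual VMR of 3 in the illustration is also at the high end. In a check of the simulated event counts, a marginal VMR of 3 left about 1.8-2.5 after baseline adjustment, and a marginal VMR of 4 left about 2.0-3.1. The VMR 2 interval in step 2 is therefore the more moderate case.

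Third, the consequence is bounded. IRR estimates are unbiased, significance is played down, means are also considered for alcohol variables, and no go/no-go rule depends on these intervals. This limits the severity, but the caveat cites sample size, not dispersion, and corrects no interval. The GEE is conditional and exploratory, and its binomial/logit form leaves the Poisson IRR intervals unchanged.

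Fourth, scaling is not the only remedy. Leverage-corrected robust standard errors with a t reference did as well for event counts (94-96%) and would also be acceptable.

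**Conclusion.** The concern holds. As written, the primary analysis misstates precision whenever residual variance differs from the mean. For sexual event counts the intervals are likely too narrow: under the log-normal-Poisson assumptions, coverage is roughly 84-88% at a marginal VMR of 2 and 70-80% at 4, with baseline adjustment that the plan does not guarantee. For days out of 30, coverage ran from 70% to 98% depending on how much men differ and how well baseline predicts follow-up. These figures rest on assumed rates, dispersions, equal allocation and no drop-out.

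This should be fixed before analysis. It is not fatal: the estimates are unaffected and the trial is a pilot.

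**What to change.** Replace the Poisson sentence in the SAP, and its counterpart in the protocol, with wording such as:

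> All count outcomes will be analysed at each follow-up by Poisson regression with standard errors scaled by the Pearson dispersion and a t reference, adjusted for the same outcome's baseline 30-day TLFB value; the estimated dispersion will be reported with each IRR. Average drinks per drinking day will be analysed by linear regression adjusted for its baseline value.

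Scaling works in both directions, so it also handles under-dispersed day counts. If yes/no secondary outcomes are compared by Poisson-based ratios, use robust standard errors or report a risk difference.

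Two definitions should be settled alongside. The listed TLFB items do not include whether a partner is new, so the baseline covariate for that outcome must be specified. Average drinks per drinking day is undefined for men with no drinking days, so their handling must be stated.

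The cost is one or two sentences and a software option. In the log-normal-Poisson simulations, event-count intervals become about 1.3-1.4 times wider on the log scale at a marginal VMR of 2 and 1.4-1.6 times at 3. They widen by 2-3% if there is no over-dispersion. Intervals for low-spread day counts (12-18 days) narrow by about 16%.

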Phase 1c: Theatre testing of BI alpha-version. We will recruit a sample of 10 MSM, using the eligibility criteria from Phase 1b, to conduct a “theatre test” of the BI. MSM who participated in earlier phases will be excluded to provide different perspectives. Participants who are seeking HIV testing at the target venues will be recruited using a screening item concerning their interest in the study that will be included on the standard post-test assessment, and their participation will be anonymous. Interested participants will simply wait in the testing room for study staff after VCT is complete. Staff will then provide them with a tablet and headphones in order to complete the full intervention. Afterward, participants will complete a brief questionnaire and interview about their perceptions of the acceptability and feasibility of delivering a BI in this environment, as well as comments they have about each BI component. Participants will receive \$30 for completing the theatre test.

Qualitative analysis. Recordings of all focus groups and interviews will be transcribed via commercially available software. Data will be analyzed using modified grounded theory methods⁹⁰, with two independent coders arriving at a consensus on major themes identified. This qualitative data will allow us to refine the assessment instruments and BI components for population sensitivity. As such, the study team will review the analysis, and assess the strengths/weaknesses of each of the components based on these findings.

C.4.2. PHASE 2: PILOT TESTING

Specific Aim 2 is to conduct a pilot randomized controlled trial of our BI, and explore preliminary evidence of its efficacy for reducing sexual risk and alcohol use among a sample of high-risk MSM seeking HIV testing in community venues. As such, we will randomize 40 MSM who receive HIV testing at the identified venues to either the standard VCT group + attention-matched control (AC), or the VCT + Intervention (BI) group. We will test the hypothesis that those in the BI group will report reductions in sex risk outcomes, sex under the influence of alcohol, and alcohol use at 1-, 3-, and 6-month follow-ups compared to the VCT+AC group.

C.4.2.1. Methods

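### Efficacy is to be judged from an undefined pattern of 12 or 15 per-visit estimates; a rate ratio averaged over follow-up, read with its CI, would be a cheap improvement

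*SAP*

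**What the plan says.** The primary-analysis text of the protocol (C.4.2.2 Data Analysis Plan) and the SAP paragraph run almost in parallel.

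- **Estimates.** The protocol plans an "intention-to-treat comparison of the rates of our primary outcomes at 1-, 3-, and 6-month follow-ups, using an incidence rate ratio (IRR) and 95% CI"; the SAP plans an "intention-to-treat comparison of the rates of our primary outcomes at 1-, 2-, and 3-month follow-ups, using incidence rate ratios (IRRs) and 95% CI". The model is stated as "Given the count nature of much of the data, we will use a Poisson regression covarying for key baseline covariates", with the arms compared separately at each time point.
- **Outcomes.** The protocol (C.4.2.2 Measures, Efficacy outcomes) says "Our primary outcomes will be the number of unprotected anal sex events, number of sex events under the influence of alcohol" and adds drinking frequency and heavy drinking days, making four. The SAP lists five: new anal sex partners, condomless anal sex events, drinking frequency, binge frequency and drinks per drinking day. Neither list is ranked.
- **Basis for the conclusion.** Both texts expect limited conclusions about significance and then say that "clinically meaningful differences in the pattern of IRRs and means (for alcohol use variables) across groups will be used to evaluate our hypotheses".
- **Across visits.** The only model is conditional: "if available data produce stable results, generalized estimating equations (GEEs) using binomial distributions and logit-link functions will also be used to explore differences".
- **Purpose.** Protocol C.4.2 says "We will test the hypothesis that those in the BI group will report reductions in sex risk outcomes" relative to control. The same section, and Specific Aim 2 in C.1, call the evidence preliminary. C.1 describes initial evidence of efficacy as groundwork for a full-scale trial.

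**The concern.** Setting significance aside in a 40-person pilot is reasonable. The difficulty is what replaces it. The hypotheses are still to be evaluated, but on a criterion with no content: no threshold, no number of outcomes or visits that must agree, and no role for the interval. The CIs are to be reported, yet the text allows efficacy to be read from point estimates alone. Someone reading the result could not tell whether the rule applied was strict or loose, or whether it was settled before the data were seen.

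The estimation plan also leaves information unused. Each person contributes three follow-up reports, but each planned IRR uses one. The GEE that would combine them has a binomial distribution and logit link. That is a sound choice for drinking days out of a 30-day Timeline Follow Back. It gives odds ratios, and it has no natural denominator for condomless sex events, sex events under the influence of alcohol, or new partners.

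**Working it through.** The documents state no error rate, threshold, mean, dispersion or dropout figure, so there is no plan figure to reproduce. What follows is a count, some closed-form checks, and ranges under stated assumptions.

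**1. Number of contrasts.** Protocol 4 × 3 = 12; SAP 5 × 3 = 15. If means are read as well as IRRs for the alcohol variables (two in the protocol, three in the SAP), the totals are 12 + 6 = 18 and 15 + 9 = 24.

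**2. Simple bound on one consistency reading.** With no effect and independent visits, an outcome favours the intervention at all three visits with probability 0.5³ = 0.125. The chance that at least one independent outcome does so is 1 − 0.875⁴ = 41% (protocol) or 1 − 0.875⁵ = 49% (SAP). Correlation between visits raises the per-outcome figure to about 18–22% in simulation. Correlation between outcomes pulls the overall figure back.

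**3. Null simulation of several readings.** Assumptions: 20 per arm, complete data, each estimate adjusted for its own baseline by Poisson regression; latent correlation between visits 0.4 or 0.6 and between outcomes 0.3 or 0.6; variance-to-mean ratio 2, 3 or 5. Sex outcomes are negative binomial (means 4 and 5). Drinking days and binge days are beta-binomial out of 30 (means 10 and 6). Drinks per drinking day is gamma (mean 6). Every estimate is read as a ratio of means.

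| Reading of a favourable pattern | SAP, 15 | Protocol, 12 |
|---|---|---|
| Two outcomes ≤0.80 at all three visits | 0–2% | 0–2% |
| One outcome ≤0.80 at all three visits | 2–12% | 2–11% |
| At least 12 of 15 (10 of 12) below 1 | 10–19% | 8–17% |
| One outcome ≤0.75 at two or more visits | 5–30% | 5–30% |
| Some outcome below 1 at all three visits | 46–61% | 42–57% |
| Any one estimate ≤0.75 | 25–76% | 23–75% |

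A second set of assumptions (all outcomes counts with mean 3 or 6, no baseline adjustment) gives 59–68% and 52–62% for some outcome below 1 at all three visits, and 31–95% and 27–91% for any one estimate ≤0.75. One outcome ≤0.75 at all three visits then reaches 29% and 26%, against at most 6% in the first set.

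**4. Gain from averaging over visits.** If any two measurements, baseline included, correlate at ρ, adjusting for baseline leaves a correlation r = ρ/(1 + ρ) between follow-ups. The variance of a three-visit average relative to one visit is (1 + 2r)/3.

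- ρ = 0.4: r = 0.286, ratio = 1.571/3 = 0.52, a cut of 48%.
- ρ = 0.6: r = 0.375, ratio = 1.75/3 = 0.58, a cut of 42%.

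Simulated ratios were 0.47–0.59, that is cuts of 41–53%. A separate run gave 0.48–0.61, that is 39–52%. Roughly 40–50% is a fair summary.

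**5. What the averaged IRR can show.** With complete data the median 95% CI was the estimate ×/÷ 1.20 to 1.71. To exclude 1, the observed IRR must fall below 1/1.20 = 0.83 in the best case and 1/1.71 = 0.58 in the worst. Power for a true IRR of 0.75 was about 17–83%, against 12–57% for one visit. If 20% were lost (16 per arm), variance rises by 20/16 = 1.25 and the log half-width by √1.25 = 1.118. The interval becomes about ×/÷ 1.20^1.118 = 1.23 to 1.71^1.118 = 1.82.

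**6. Choice of variance.** With variance-to-mean ratios of 2–5, a plain Poisson CI at one visit was falsely favourable in 4–17% of null trials. A small-sample robust CI on the three-visit IRR was so in about 2–3.5%, close to the nominal 2.5%.

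**The case against.** The strongest reply is that this is an exploratory pilot. The protocol speaks of preliminary effects and preliminary evaluation, warns that significance conclusions will be limited, and plans a CI at every visit, so a reader would see the precision of each estimate. It does not claim a controlled error rate. It also hypothesises effects at each of three visits, and one average is a different question. All of this stands, and it is why the point is modest. It does not supply the missing rule: the text still evaluates hypotheses on a pattern it does not describe.

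Four stronger readings should be resisted.

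- *A reader might infer that the plan has a high false-positive rate.* It states no rule, so it has no rate. The table shows what different rules would imply under assumptions that are not the trial's.
- *A reader might infer that asking for consistency across visits is enough protection.* It is not. Some outcome lies below 1 at all three visits in 42–61% of null trials.
- *A reader might set 2–3.5% against the table and credit pooling with the fall.* That compares a CI rule with point-estimate cut-offs. Judged by point estimate, at least one of two averaged IRRs (one per domain) is ≤0.80 in 6–26% of null trials. Protection comes from using the interval; averaging adds precision.
- *A reader might infer that no longitudinal model is planned, or that the pilot is a formal go/no-go gate.* A GEE is planned, conditionally, and C.1 sets no such gate.

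**Conclusion.** The point holds as a cheap improvement. The criterion for the efficacy hypotheses is undefined, the per-visit estimates are unranked, and no rate ratio averaged over visits is planned for the unbounded counts. Depending on the reading adopted, a favourable result under no effect ranges from a few percent to about half or more.

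All simulated rates rest on assumed means, dispersion, correlations, equal arms and, unless stated, complete data. They show how much the conclusion depends on the rule; they are not properties of this trial. The 40–50% variance reduction is a gain in precision for each outcome, not control of a trial-wide error rate. If four or five outcomes were each read by their own 95% CI, at least one would be falsely favourable in up to about 1 − 0.975⁴ = 10% or 1 − 0.975⁵ = 12% of trials if they were independent. Dropout would reduce precision further.

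**What to change.** Reconcile first the visit months (1, 3, 6 against 1, 2, 3) and the outcome lists (four against five). That is a separate defect and adds no weight here. Then:

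1. For the count outcomes, replace the binomial/logit GEE with a log-link (Poisson) repeated-measures model, adjusted for the baseline value of the outcome, with small-sample-corrected robust variance. It should give one IRR averaged over the three follow-ups. Keep the binomial GEE only for drinking days out of 30.
2. Replace the pattern sentence with: *Each hypothesis is interpreted from this IRR and its 95% CI; efficacy is not claimed from point estimates alone, and a CI that includes 1 is reported as inconclusive.* Drinks per drinking day is an average and not a count, so state the corresponding ratio or difference of means and read it with its CI in the same way.
3. Report per-visit IRRs and means as descriptive.

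Naming one lead outcome per domain from those in both lists (condomless anal sex events; heavy or binge drinking days) is advisable. It would demote other outcomes that the plan calls primary, so it is the sponsor's choice.

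The cost is SAP wording and one model per outcome, with no new data. Averaging can mask decay, which is why the per-visit results stay. With 40 people the CI will often be inconclusive, and the report should say so.
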